###### **Combined20130356,20110100&20140159Studies**

Treatment-emergent adverse events are defined as adverse events that occurred on or after day 1 of cinacalcet treatment in the parent study (Studies 20140356 and 20110100) or Study 20140159.

##### Events of interest (EOI)

The EOI names and search scopes (provided by Amgen Global Safety) are listed below:

EOI Name	Scope
Acute pancreatitis (SMQ)	Narrow
Cardiac failure (SMQ)	Narrow
Convulsions (SMQ)	Broad
Drug related hepatic disorders - comprehensive search (SMQ)	Narrow
Fractures (Amgen MedDRA Search Strategy)	Narrow
Hypersensitivity (SMQ)	Narrow
Hypocalcemia (Amgen MedDRA Search Strategy)	Narrow
Hypotension (Amgen MedDRA Search Strategy)	Narrow
Ischaemic heart disease (SMQ)	Narrow
Malignant or unspecified tumors (SMQ)	Narrow
Medication errors (SMQ)	Broad
Product use issues (MedDRA HLGT)	Broad
Nervous system disorders excluding seizures (Amgen MedDRA Search Strategy)	Broad
Torsade de pointes/QT prolongation (SMQ)	Narrow
Ventricular tachyarrhythmias (SMQ)	Narrow

Change from **studybaseline**

For each subject, change from **study** baseline for a given variable at a given time point or periods is defined as:

$$(\text{Value at the given time point or period} - \text{study baseline value})$$

and will be calculated at the same number of decimal places as the raw data provided by laboratory where applicable.

Percent change from **studybaseline**

For each subject, percent change from **study** baseline in a given variable at a given time point is defined as:

$$100 \times ((\text{value at the given time point or period} - \text{study baseline value}) / \text{study baseline value})$$

and will be calculated to one decimal place.

Change from day 1 of cinacalcet treatment

For each subject, change from baseline at first cinacalcet dose for a given variable at a given time point or period is defined as:

$$(\text{Value at the given time point or period} - \text{baseline at first cinacalcet dose})$$

and will be calculated at the same number of decimal places as the raw data provided by laboratory where applicable.

Percent change from day 1 of cinacalcet treatment

For each subject, percent change from baseline at first cinacalcet dose in a given variable at a given time point or period is defined as:

$$100 \times ((\text{value at the given time point or period} - \text{baseline at first cinacalcet dose}) / \text{baseline at first cinacalcet dose})$$

and will be calculated to one decimal place.

Growth velocity

Linear growth velocity (cm/year) =  $52 \times \text{change in height (cm)} / \text{number of weeks}$   
between the two assessments.

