# 3.5 Estimated Study Duration

# 3.5.1 Study Duration for Subjects

The total duration for this study is 32 weeks; a 28-week treatment period and 4-week safety follow-up period.

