# 7.2.5 Early Termination

Subjects who discontinue participation in the study prior to week 28 will be asked to complete an early termination visit and should have all EOIP and EOS evaluations performed as outlined in the Schedule of Assessments and in Sections 7.2.4 and 7.2.6.

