#### 7.3.4 Physical Exam, Height, Tanner Stage, Dry Weight

A physical exam will be performed on day 1. Breast, genital, and rectal examinations are not required for any study visit unless specific evaluation is warranted.

The physical examination at the EOS visit will consist of a follow-up examination to monitor for any changes from the day 1 physical examination. Any clinically significant changes in the physical examination per the investigator's opinion should be recorded on the adverse event eCRF.

Information regarding the subject's residual urine output will be collected on day 1.

Height will be collected on day 1 and at the EOS visit and should be measured with the subject's shoes removed.

Tanner stage will be determined on day 1 and at the EOS visit and recorded in the eCRF.

AMGE

Page 50 of 79

The subject's dry weight should be collected at day 1 and at the EOS visit post-dialysis for hemodialysis subjects and at the study visit, while the peritoneal cavity is empty, for peritoneal dialysis subjects. For all subjects the weight is to be measured with the subject wearing light clothing and with his/her shoes removed.

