# 10.4 Planned Methods of Analysis

# 10.4.1 General Considerations

There is no formal statistical testing for this study. The analysis for all endpoints will be descriptive in nature. Descriptive statistics will be used to summarize data for continuous variables (including n, mean, standard deviation (SD) or standard error (SE), median, 25th (Q1) and 75th (Q3) percentiles, and minimum and maximum values, where applicable).

For categorical variables, the number and percentage of subjects in each category will be reported. Graphical presentations may be provided for selected variables.

All summary tables will be provided by study treatment group: Study 20130356 (SOC, SOC + cinacalcet) and Study 20110100 and overall, unless otherwise specified.

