**10.6.3 Analyses of Exploratory Endpoints**

**20140159 study only**

**Analyses of exploratory endpoints will be based on Efficacy Analysis Set.** Growth velocity and change in Tanner stage from **Study Day 1 in study 20140159 to end of study** will be summarized using descriptive statistics. **The analysis will only include subjects who have growth velocity values available or tanner stage assessments available at both Study Day 1 in study 20140159 and end of study; no imputation will be done for missing values.**

**Actual values, change and percent change of iPTH, serum cCa, serum phosphorus and CaxP values at scheduled visits from study baseline for all Efficacy Analysis Set subjects through last dose of IP+7 days will be summarized and presented graphically.**

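### Growth velocity is annualised with no minimum interval and left out of the age-band subgroups, so a few early leavers can distort the mean and SD and the overall column mixes ages

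*SAP*

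**What the plan says.** **Definition.** SAP 6.4 gives "Linear growth velocity (cm/year" as 52 times the change in height in cm, divided by the weeks between the two assessments. It sets no lower limit on that interval, and none of the analysis windows in SAP 6.2 names height.

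**When height is measured.** Protocol 7.3.4: "Height will be collected on day 1 and at the EOS visit". The planned interval follows from Protocol 3.5.1: "The total duration for this study is 32 weeks". Protocol 7.2.5 adds that "Subjects who discontinue participation in the study prior to week 28 will be asked to complete an early termination visit", and that they "should have all EOIP and EOS evaluations performed as outlined". The end-of-study list in Protocol 7.2.6 includes height.

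**Who is analysed.** SAP 10.6.3: "The analysis will only include subjects who have growth velocity values available or tanner stage assessments available" at both time points, without imputation. SAP 9.5 keeps every outlier that is not a known error.

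**How it is reported.** Protocol 10.4.1: "All summary tables will be provided by study treatment group: Study 20130356 (SOC, SOC + cinacalcet) and Study 20110100 and overall, unless otherwise specified". SAP 7.3 says more loosely that subjects are analysed by the treatment received in the parent studies, and overall. The optional age bands (Protocol 10.1.3, SAP 7.7) apply to primary, secondary and safety endpoints. Growth is exploratory and is not among them.

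**The concern.** Annualising a short interval multiplies the measurement error along with the growth. A subject who leaves in the first weeks contributes a velocity that is mostly reading error, and it counts as much as a completer's value in the mean and SD. The error can have either sign, so the mean may move either way while the SD can only grow.

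Growth velocity also depends strongly on age, yet no age-banded, age-standardised or sex-standardised growth summary is planned. An overall mean from infancy to adolescence then partly reflects how many subjects each parent study supplied.

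Linear growth is half of the only exploratory objective. What is at stake is whether the growth summary can be interpreted. No test or decision depends on it.

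**Working it through.** **The plan's own figure.** SAP 3.2: 48 + 30 = 78 subjects, which reproduces. The plan states no expected velocity, height error, SD or dropout rate, so those inputs below are assumptions.

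**1. Multiplier and error per subject.** With *s* the SD of one height reading (assumed 0.3 to 0.5 cm), the error SD of velocity over *w* weeks is (52/*w*) × √2 × *s*.

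| Weeks between heights | 52/*w* | Error SD, *s* = 0.3 (cm/yr) | Error SD, *s* = 0.5 (cm/yr) |
|---|---|---|---|
| 32 | 1.625 | 0.69 | 1.15 |
| 12 | 4.33 | 1.84 | 3.06 |
| 4 | 13 | 5.52 | 9.19 |

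The variance ratio of 4 weeks to 32 weeks is (32/4)² = 64, and *s* cancels.

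**2. Leavers' share of within-group variance.** Further assumptions: true velocity SD 2 cm/yr, a fraction *p* leaving early and supplying a closing height, exits uniform over the stated weeks. The parts are:

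- leavers' error: L = *p* × 2*s*² × mean of (52/*w*)²
- completers' error: C = (1 − *p*) × 2*s*² × 1.625²
- true variation: B = 2² = 4
- share = L / (L + C + B)

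Example with *p* = 10%, *s* = 0.5, weeks 1 to 28: the mean of (52/*w*)² is 155.5. L = 0.10 × 0.5 × 155.5 = 7.77, C = 0.90 × 0.5 × 2.64 = 1.19, and the share is 7.77/12.96 = 60%.

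| Leavers | Exits weeks 1–28, *s* = 0.3 / 0.5 | No exit before week 4, *s* = 0.3 / 0.5 |
|---|---|---|
| 5% | 24% / 43% | 5% / 11% |
| 10% | 39% / 60% | 10% / 21% |
| 20% | 56% / 75% | 18% / 35% |
| 30% | 66% / 83% | 25% / 45% |

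**3. Effect on the reported statistics.** Simulation (4,000 runs) of a group of 24 with 20% leavers and exits from week 1, SE in cm/yr for *s* = 0.3 / 0.5:

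- mean: 0.64 / 0.96
- median: 0.55 / 0.62
- mean of completers only: 0.48 / 0.52

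**4. Age mix in the overall column.** With 30 younger and 48 older subjects, a difference *d* between the parent-study means adds (30/78)(48/78)*d*² to the variance. With 10% leavers and *s* = 0.3, the within-group variance is 2.69² = 7.24. Age mix then supplies 3% of the overall variance at *d* = 1 cm/yr, 23% at 3, 45% at 5 and 68% at 8. The values of *d* are assumptions.

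**5. Combined analysis.** From day 1 of cinacalcet, subjects who completed cinacalcet in a parent study have a planned interval of about 20 + 32 = 52 or 26 + 32 = 58 weeks (multiplier 1.00 or 0.90). For former standard-of-care subjects, SAP 6.3 sets the baseline at extension Study Day 1, so they gain nothing.

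**6. Candidate remedies.** With 10% to 20% leavers and *s* = 0.3 to 0.5, leavers' share without a minimum is 39% to 75%. A 12-week minimum brings it to 2% to 10%, and a 24-week minimum to about 0% to 2%. A pooled ratio (sum of height change / sum of weeks × 52) keeps everyone: for 78 subjects, 20% leavers and *s* = 0.5, its SE is 0.28 against 0.52 for the plain mean.

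**The case against.** A reader might infer that early leavers' error will dominate the growth summary. The documents do not support that. The 64-fold ratio compares two individual subjects and says nothing about how many short intervals will occur. The share passes one half only with several exits in the first weeks or larger reading error.

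Very short intervals are also harder to reach than they look. Transplant, parathyroidectomy and adverse events end treatment (Protocol 8.2.1), not study participation (8.2.2), and a 4-week follow-up is planned after treatment. Death and loss to follow-up would normally yield no closing height. This narrows the problem but does not remove it: subjects who withdraw, or whom the sponsor removes, are still asked for the visit.

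A reader might also infer that infants and adolescents are averaged throughout. They are not. The Protocol 10.4.1 columns follow parent study and arm, which separates subjects enrolled under 6 years from those enrolled at 6 or over. The full mix arises only in the overall column, and nothing says that column will lead the report. The parent-study columns nevertheless span 28 days to under 6 years and 6 to under 18 years.

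SAP 9.6 and 10.1 plan the median, quartiles, minimum and maximum alongside the mean and SD. That stands as real protection for the median, but the mean and SD will still be reported. The longer interval in the combined analysis also stands, though only for subjects given cinacalcet in a parent study.

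Finally, a 24-week cut has no basis in the documents, and excluding early leavers selects on retention. Both points are fair and shape the fix.

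**Conclusion.** The point holds as a low-severity improvement. No minimum interval is set, early-termination heights enter with equal weight, and growth is missing from the age bands; all three follow directly from the text. The 64-fold variance ratio needs no assumption about reading error. The effect on the group summary does: leavers' error could be about 5% or as much as 83% of within-group variance, depending on assumed reading error (0.3 to 0.5 cm), true SD (2 cm/yr), leaver fraction (5% to 30%) and exit timing. The defensible claim is that a few short intervals *can* distort the mean and SD, chiefly in the extension-only summary and for former standard-of-care subjects. The size of the age effect in the overall column likewise rests on an assumed difference between the parent studies. The endpoint is exploratory, descriptive and reported only at the final analysis, so the consequence is limited to how the growth result can be read.

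**What to change.** Amend SAP 6.4, 7.7 and 10.6.3 before the final analysis:

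1. Add growth velocity to the endpoints summarised by the SAP 7.7 age bands, alongside the parent-study and arm columns of Protocol 10.4.1.
2. Compute velocity only when the two heights are at least a pre-specified number of weeks apart, and list shorter intervals as raw height change with the weeks elapsed. Twenty-four weeks is one reasonable choice; 12 weeks already removes most of the excess error and keeps more subjects.
3. As a check that retains early leavers, report within each age band the pooled ratio: sum of height change divided by sum of weeks, times 52.

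The cost is SAP wording only, with no new visits or data. The velocity summary loses a few subjects and selects on retention, which the pooled ratio addresses. The bands are still fairly wide (28 days to under 2 years; 12 to under 18 years) and some may be small, so they reduce the age mix without removing it. Setting the rule in advance also avoids deciding after seeing the data which velocities to leave out.

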## 6.5 Derived Variables

### Corrected total serum calcium

Corrected total serum calcium (mg/dL) = measured total serum calcium (mg/dL) + 0.8  
(4.0 – Serum albumin (g/dL)), or

Corrected total calcium (mmol/L) = measured total serum calcium (mmol/L) + 0.02  
(40 – Serum albumin (g/L)).

Total serum calcium will only be corrected using above formulae if the serum albumin is < 4 g/dL or 40 g/L. The correction will be done at the Covance central lab.

### IP compliance

Daily subject compliance with administration of cinacalcet is documented on the IP administration eCRF. IP compliance (%) = 100 x (number of days of planned dosing – number of days dose is changed due to noncompliance) / number of days of planned dosing.

### Actual treatment

**Actual treatment of a subject in Study 20140159 is cinacalcet if the subject received at least one dose of IP, and is missing if the subject did not receive any IP throughout the study.**

## 7. Analysis Subsets

### 7.1 Full Analysis Set

**The Full Analysis Set (FAS) includes all Study 20140159 enrolled subjects.** All subjects will be analyzed according to the actual treatment **received** in the parent studies and overall.

### 7.2 Safety Analysis Set

The Safety Analysis Set will be used for primary and safety endpoints. It includes all subjects who were enrolled in Study 20140159 and received at least one dose of investigational product. **Subjects will be analyzed according to the treatment received in the parent studies and overall.**

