#### 103 Subjects on anti-convulsant medication must be on a stable dose

#### All subjects from 20130356

- 104 Completed treatment through week 20 in the 20130356 study or on study at the time of Study 20130356 termination
- 105 Dry weight ≥ 12.5 kg at day 1 of Study 20140159

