#### 4.1.2 Exclusion Criteria

General

Studies 20130356 or 20110100

- 201 Currently receiving treatment in another investigational device or drug study, or less than 30 days since ending treatment on another investigational device or drug study(s), other than Amgen Studies 20130356 or 20110100.
- 202 Other investigational procedures while participating in this study are excluded.
- 203 Malignancy except non-melanoma skin cancers, cervical or breast ductal carcinoma in situ within the last 5 years.
- 204 Subject has known sensitivity to any of the products to be administered during dosing.
- 205 Subject likely to not be available to complete all protocol-required study visits or procedures, and/or to comply with all required study procedures (eg, electronic patient diary [ediary]) to the best of the subject and investigator's knowledge
- 206 History or evidence of any other clinically significant disorder, condition or disease (with the exception of those outlined above) that, in the opinion of the investigator or Amgen physician, if consulted, would pose a risk to subject safety or interfere with the study evaluation, procedures, or completion.
- 207 Subject previously has entered this study.
- 208 If sexually active, subject is not willing to use acceptable contraception during treatment and for at least 9 days after the end of treatment.
- 209 Subject is pregnant or breast feeding, or planning to become pregnant during the study or within 9 days after the end of treatment
- 210 History of congenital long QT syndrome, second or third degree heart block, ventricular tachyarrythmias, or other conditions associated with prolonged QT interval

Page 22 of 79

211 A new onset of seizures or worsening of pre-existing seizure disorder

All Subjects with > 14 days between the last study visit in Study 20130356 or Study 20110100 and the screening visit in Study 20140159 will have the following exclusion criteria applied during screening and day 1:

- 212 Unstable chronic heart failure defined as worsening pulmonary edema or other signs and symptoms as per investigator assessment during screening
- 213 Received therapy with commercial cinacalcet after the last study visit in Study 20130356 or Study 20110100 before day 1 of Study 20140159
- 214 Scheduled date for kidney transplantation from a known living donor that makes completion of the study unlikely

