**Time of follow-up (in days: use for follow-up adjusted AE for the final analysis)**

End of study date – Day 1 of cinacalcet treatment +1

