#### **10.5 Analysis of Primary Endpoint**

The primary endpoint is incidence of treatment emergent adverse events of interest as defined in **Section 6.4**. The analysis will be based on Safety Analysis Set. Subject incidence of EOIs will be summarized by EOI category and **preferred term for data in Study 20140159 only for both the interim and final analyses. The 95% confidence intervals (CI) of the overall subject incidence rates will be reported.**

**The secondary analysis of the primary endpoint is follow-up time adjusted incidence of EOIs for combined data from parent studies and data from the 20140159 study for the final analysis.**

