**Combined 20130356, 20110100 & 20140159 studies**

**Proportion of subjects achieving the secondary endpoints of  $\geq 30\%$  reduction in iPTH from day 1 of cinacalcet treatment to mean value during weeks 11 and 15 will be reported with 95% CI for all efficacy analysis set subjects. Subjects who have no weeks 11 or 15 iPTH values will be considered non-responders.**

**Proportion of subjects achieving the secondary endpoints of  $\geq 30\%$  reduction in iPTH from day 1 of cinacalcet treatment to mean value during weeks 23 and 28 will be reported with 95% CI for all efficacy analysis set subjects. For subjects who do not have an iPTH value during weeks 23 and 28, the mean of the last two available post-baseline values collected at protocol-specified visits in the dose titration phase will be used. If only one post-baseline value is available, this single value will be used. If no post-baseline value is available, the subject is considered a non-responder.**

**Summary statistics will be provided for percent change in iPTH, change in serum cCa and change in serum phosphorus over time from day 1 of cinacalcet treatment for all efficacy analysis set subjects.**

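### The combined follow-up-adjusted EOI and AE rates count parent-study cinacalcet time only for children who rolled over, so they run low for events that bar entry to 20140159

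*SAP*

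**What the plan says.** SAP 7.2 defines the Safety Analysis Set: "It includes all subjects who were enrolled in Study 20140159 and received at least one dose of investigational product". SAP 10.5 puts the EOI analysis on that set ("The analysis will be based on Safety Analysis Set") and names no other for its second part, the "follow-up time adjusted incidence of EOIs for combined data from parent studies and data from the 20140159 study for the final analysis". SAP 10.7, which holds the combined AE and EOI table (10.7.1), also defaults to the Safety Analysis Set.

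The combined clock starts earlier than the set does. SAP 6.1 defines follow-up for the adjusted rates as "End of study date – Day 1 of cinacalcet treatment +1". SAP 6.4 counts combined treatment-emergent events from the first day of cinacalcet, in the parent study where that applies. The end-of-study date in SAP 6.2 is an extension date, so a child who did not roll over has no follow-up time under this plan.

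Entry to the extension is selective. From 20130356 a child must have "Completed treatment through week 20 in the 20130356 study or on study at the time of Study 20130356 termination"; the condition for 20110100 is parallel, at week 26. Protocol 4.1.2 then excludes, for all subjects:

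- malignancy within 5 years, with listed exceptions (203);
- a history of ventricular tachyarrhythmia or of conditions linked to QT prolongation (210);
- "A new onset of seizures or worsening of pre-existing seizure disorder" (211);
- an ongoing event related to the product that is grade 3 or higher and/or clinically significant (217);
- a day-1 QTc above 500 ms (219).

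SAP 6.4 lists convulsions, ventricular tachyarrhythmias, torsade/QT prolongation and malignant tumours among its 15 EOI searches.

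**The concern.** Parent-study person-time enters the combined rate only if the child later enrolled and was dosed in 20140159. This is immortal-time selection: membership of the set depends on what happened during the time being counted. A child who had a first seizure on cinacalcet in a parent study and was therefore excluded leaves both numerator and denominator. So does a child who died, one who withdrew early, and one who enrolled on a dose hold and was never re-dosed. The parent time that remains comes from children who did not have a barring event.

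The combined EOI and AE rates are the plan's follow-up-adjusted event rates over cumulative cinacalcet exposure, and the primary objective is long-term safety. As defined, they describe children who did well enough on the drug to continue. SAP 9.4 undertakes to look at the timing of and reasons for withdrawal, and at biases discussed in the parent SAPs. It does not name roll-over selection and plans no corrective analysis.

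**Working it through.** **Inputs.** 20130356: about 48 children randomised 1:1, so 24 on cinacalcet and 24 on standard of care (SOC); 20-week treatment period, with the 4-week follow-up waived on roll-over (protocol 2.5.1). 20110100: 30 children (SAP 3.2) for 24 + 2 = 26 weeks (protocol 2.5.2). Extension: 32 weeks (protocol 3.5.1). SOC children start cinacalcet in the extension and bring no parent cinacalcet time.

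**Plan's own figure.** 48 + 30 = 78, as SAP 3.2 states. It presumes that every parent subject rolls over.

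**Share of combined time that lies in the parent studies.**

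- Parent time: 24 × 20 + 30 × 26 = 480 + 780 = 1260 person-weeks.
- Extension time: 78 × 32 = 2496 person-weeks.
- Pooled share: 1260 / (1260 + 2496) = 1260 / 3756 = 33.5%.
- Among the 54 parent-exposed children: 1260 / (1260 + 54 × 32) = 1260 / 2988 = 42.2%.

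**Bias.** Let *s* be the parent share of time and *q* the share of children with the event in the parent study who do not roll over. With a constant hazard and an uncommon event, the rate under the SAP's set relative to the rate in all cinacalcet-treated children is about 1 − *q* × *s*. Neither *q* nor an EOI rate is in the documents, so both are assumed over a range.

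| *q* | Pooled (*s* = 0.335) | Parent-exposed (*s* = 0.422) |
|---|---|---|
| 0 | 1.00 | 1.00 |
| 0.25 | 0.92 | 0.89 |
| 0.5 | 0.83 | 0.79 |
| 1 | 2496/3756 = 0.66 | 1728/2988 = 0.58 |

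**Check without the uncommon-event approximation.** A closed-form calculation used the SAP's follow-up definition, removed the non-rollers, and assumed first-event rates of 0.05, 0.2 and 0.5 per patient-year. Pooled ratios were 0.917 to 0.921 (*q* = 0.25), 0.833 to 0.841 (*q* = 0.5) and 0.665 to 0.672 (*q* = 1). Among the parent-exposed, *q* = 1 gave 0.569 to 0.577. For example, at 0.2 per patient-year and *q* = 1 the SAP's set gives 12.6 events per 100 patient-years, against 18.9 in all exposed children.

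**Reverse case.** If every child with the event rolled over and 20% of event-free children left, for instance for transplant, the pooled ratio would be 1.06 to 1.08.

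**The case against.** The strongest reply is about scope. The primary analysis of the primary endpoint uses 20140159 data only and counts no parent time. What is affected is descriptive and confined to the final analysis.

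The overlap between entry criteria and EOIs is also partial. Criterion 219 is a day-1 reading, and 220 allows 450 to 500 ms with written permission. Criterion 217 needs an event that is both ongoing and related. Criterion 211 does not cover stable recurrence in a known seizure disorder. Criterion 204 concerns sensitivity to the study products, not any hypersensitivity event. Heart failure, recent ventricular arrhythmia needing a treatment change, and hepatic impairment (212, 215, 216) are screened only after a gap of more than 14 days. A child on dose hold at the end of the parent study may still enrol (protocol 4), so selection is weakest for hypocalcaemia, the main stated risk. All of this stands. It limits the firm conclusion to events that bar entry.

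A reader might infer that the combined EOI rate as a whole is about a third too low. The documents do not support that: the figure is a ceiling for an event that always bars entry, and the reverse case shows that the direction is not fixed for other events.

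A reader might also infer that the combined ≥ 30% iPTH response is inflated. Those endpoints are conditioned on roll-over too, through the Efficacy Analysis Set (SAP 7.3). But the SAP 10.6.1 rule is narrow: "Subjects who have no weeks 11 or 15 iPTH values will be considered non-responders". A child who left after week 11, or who completed the parent study without entering the extension, has values and would be scored on them. For 20130356 cinacalcet subjects, weeks 23 and 28 fall after the 20-week parent period, so the position differs again. Neither the size nor the direction of any effect on response can be derived.

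Finally, protocol 10.4.2 speaks of combined parent and extension data, which could be read more widely. The same section fixes the Safety Analysis Set, and no wider set is defined anywhere.

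**Conclusion.** The point holds for the combined follow-up-adjusted EOI and AE rates. For EOIs that bar entry (new or worsening seizures, ventricular tachyarrhythmia or QT conditions, malignancy, and ongoing related events that are grade 3 or higher and/or clinically significant), downward bias follows from the definitions whenever affected children fail to roll over. Its size depends on how often they do: from none if roll-over is unrelated to the event to about one third if the event always prevents it (42% among the parent-exposed). These figures rest on the planned numbers and visit schedules, a constant hazard, and assumed non-roll-over shares. For other EOIs, including hypocalcaemia, downward bias is plausible but unproven. The primary EOI analysis stands as planned. The change should be made before the final analysis.

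**What to change.** For the combined EOI and AE rates, define a combined cinacalcet-exposed set: every subject given at least one cinacalcet dose in 20130356, 20110100 or 20140159, whether or not they entered the extension. Run person-time from the first cinacalcet dose to the end of each subject's own AE collection.

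Use the same population for the combined iPTH responder endpoints. Score children who left on their available week values, and as non-responders only where SAP 10.6.1 says so.

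If a roll-over-only table is kept, label it as conditional on roll-over and start its clock at Study Day 1 of 20140159. A short table of non-roll-over by reason and prior EOI would let readers judge the selection.

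The cost is a SAP definition, some extra programming on parent-study data that the sponsor already plans to combine, and possibly less favourable rates. The parent studies' AE collection windows and coding are not in these documents and would need to be checked for compatibility.
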